7.10 Pharmacokinetic/Pharmacodynamic Analysis

7.10.1 Pharmacokinetic Analysis

7.10.1.1 Serum modakafusp alfa Concentrations

Blood samples will be collected at prespecified time points as described in the study protocol for the measurement of serum modakafusp alfa concentrations. Individual serum concentration data will be listed by patient, dose level, study day, and sampling time. Both nominal (scheduled) and actual sampling times will be presented in the listings.

Serum modakafusp alfa concentrations will be summarized by nominal time post dose, grouped by dose level, and study day by phases (escalation and expansion). Summary statistics will be reported at nominal sampling times with at least 2 patients in the PK evaluable population; means will be reported if the number of observations above the lower limit of quantitation (NALQ) is $\geq 50\%$ of the number of patients. The summary statistics will consist of: N, NALQ, arithmetic mean, standard deviation (SD), coefficient of variation (CV), geometric mean, CV of geometric mean, median, min, and max. Arithmetic mean, geometric mean, median, min, and max will be reported on at least 2 non-missing values, while the SD and CV will be reported on at least 3 non-missing values. modakafusp alfa concentrations that are below the limit of quantitation (BLQ) will be set to zero for calculation of summary statistics, except for geometric means, where BLQ values will be considered missing.

Concentration data that are considered anomalous may be excluded from the concentration summaries and plots. Evidence or explanations will be provided in the clinical study report to justify the exclusion of concentration data.

Mean and individual serum modakafusp alfa concentration data will be plotted over nominal sampling time, grouped by dose level, and study day on both linear and semi-logarithmic scales. BLQ values will be plotted as zero on a linear scale and treated as missing on a semi-logarithmic scale.

7.10.1.2 Serum PK Parameters

The serum PK concentration-time course data will be used to calculate standard PK parameters using noncompartmental methods with Phoenix WinNonlin.

Actual sampling times will be used for the calculation of PK parameters. In the event that actual collection times are either unreliable or missing, nominal collection times will be used. For the calculation of PK parameters, serum concentrations of modakafusp alfa that are BLQ will be treated as zero prior to t_{\max} , missing between t_{\max} and the time of the last measurable concentration, and the concentration-time curve will be considered to have terminated at the time

of the last measurable concentration. If measurable concentrations are near the lower limit of quantification (LLOQ) or imbedded between BLQ concentrations, these values may be excluded at the discretion of the Clinical Pharmacologist. Concentration data that are considered anomalous may not be used in the calculation of PK parameters; evidence or explanations will be provided in the clinical study report to justify the exclusion of data.

The PK parameters including but not limited to the parameters listed below will be determined, as permitted by data:

- C_{max} .
- t_{max} .
- AUC_{∞} .
- AUC_{last} .
- λ_z .
- $t_{1/2z}$.
- CL.
- V_{ss} .
- Accumulation ratio based on AUC_{τ} .

Individual PK parameters will be presented in listings PK parameters, and will be summarized and grouped by dose level, and study day for patients in the Cycle 1 Day 1 (C1D1) and on Cycle 2 Day1 (C2D1) for dose escalation phase (phase 1b) and on Cycle 1 Day 1 (C1D1) and Cycle 3 Day 1 (C3D1) for the phase 2 safety lead-in phase of dose expansion. Arithmetic mean, geometric mean, median, min, and max will be reported on at least 2 non-missing values, while the SD and CV will be reported on at least 3 non-missing values. Except for t_{max} , the summary statistics will consist of: N, mean, SD, CV, geometric mean, CV of geometric mean, median, min, and max. The summary statistics for t_{max} will consist of: N, median, min, and max.

In addition, box plots will be generated for C_{max} versus dose and AUC versus dose for Cycle 1 Day 1 (C1D1) and Cycle 2 Day 1 (C2D1) for dose escalation phase (phase 1b) and Cycle 1 Day 1 (C1D1) and Cycle 3 Day 1 (C3D1) for the phase 2 safety lead-in phase of dose expansion.

Dose proportionality of the PK of TAK-573 will be evaluated by visual inspection of plots of individual PK parameter values versus dose. If data permit, regression analysis using a power model will also be used to assess dose proportionality.

The PK data collected in this study are intended to contribute to future population PK analyses of modakafusp alfa. These population PK analyses may include data collected in other modakafusp alfa clinical studies. The analysis plan for the population PK analysis will be separately defined, and the results of these analyses will not be reported in the clinical study report.

7.10.2 PK/QTc Analysis

The PK-time matched triplicate ECG data collected in each patient during the dose escalation phase will be pooled to understand the PK-QTc interval relationship of modakafusp alfa. The relationship between modakafusp alfa serum concentration and effects on heart rate and QTcF interval will be analyzed using proper modeling. These population PK-QTc interval analyses may include data collected in other modakafusp alfa clinical studies. As such, the analysis plan for the population PK-QTc interval analysis will be separately defined, and the results of these analyses will be reported separately and not presented in the clinical study report for this study.

7.10.3 Pharmacodynamic Analysis

During the clinical development of modakafusp alfa, several biomarkers will be assessed to test for their correlation with safety and efficacy, if possible. Markers that will be studied are markers linked either to the drug itself or to the treated disease.

Attempts will be made to evaluate potential relationships between both modakafusp alfa dose and modakafusp alfa serum exposure versus safety and efficacy data. These analyses will be exploratory in nature.

A pharmacodynamic analysis will be included in CSR only if there is a trend.

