13.6 Pharmacodynamic Analysis

During the clinical development of modakafusp alfa, several biomarkers will be assessed to test for their correlation with safety and, if possible, with efficacy. Markers that will be studied are markers linked either to the drug itself or to the treated disease. Markers of immune system activation will be summarized using descriptive statistics. Individual data will be listed. Summaries will be provided separately for each study phase and by dose, as applicable.

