5.2 Secondary Endpoints

The secondary endpoints are:

- MTD or PAD (as defined in Section 6.1.1 of Protocol Amendment 4), if available (phase 1b).
- RP2D for SA and in combination with pembrolizumab, respectively (phase 1b and phase 2 safety lead-in).
- Frequency and severity of TEAEs according to the NCI CTCAE v.5 (phase 2 expansion).
- Number/percentage of patients with 1 or more SAEs (phase 2 expansion).
- Number/percentage of patients with 1 or more TEAE leading to dose modification and/or treatment discontinuation (phase 2 expansion).
- PK parameters after the first dose of modakafusp alfa on Cycle 1 Day 1 (C1D1) and on Cycle 2 Day 1 (C2D1) for dose escalation phase (phase 1b) and on Cycle 1 Day 1 (C1D1) and Cycle 3 Day 1 (C3D1) for the phase 2 safety lead-in phase of dose expansion, including but not limited to:
 - Maximum observed concentration (C_{\max}).
 - Time of first occurrence of C_{\max} (t_{\max}).
 - Area under the plasma concentration versus time curve from time 0 to time t (AUC_t).
 - Area under the concentration-time curve from time 0 to infinity (AUC_{∞}).
 - Terminal disposition phase half-life ($t_{1/2z}$).
 - Clearance.

- Volume of distribution at steady state (V_{ss}).
- Overall response rate (ORR) (complete response [CR] + partial response [PR]) assessed according to the mRECIST v1.1 for patients in dose escalation (phase 1b).
- Disease control rate (DCR) (CR + PR + stable disease [SD]) (phase 1b and phase 2).
- Duration of response (DOR) (phase 1b and phase 2).
- Time to progression (TTP) (phase 1b and phase 2).
- Progression-free survival (PFS) assessed according to mRECIST v1.1 (phase 1b and phase 2).
- Overall survival (OS) (phase 1b and phase 2).
- Efficacy measures of ORR, DCR, DOR, TTP, and PFS based on iRECIST (phase 2 expansion)
- Anti-modakafusp alfa antibody incidence and titer (phase 1b and phase 2).

Definitions and timeframes of primary and secondary endpoints are provided in protocol Section 6.3.3.

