7.11 Other Outcomes

7.11.1 Immunogenicity Analysis

The immunogenicity of modakafusp alfa will be assessed by determining anti-modakafusp alfa antibody incidence and characteristics (e.g., titer and specificity). All ADA data will be listed. For patients in the immunogenicity evaluable analysis set, percent of patients with positive ADA at each timepoint, as well as percent of patients with positive ADA by domain specific assay and ADA titers, will be summarized by dose levels by study phases (escalation and expansion). Percent of patients with positive ADA at baseline and at any post-baseline time point during the study will be reported. Additional summary tables and figures may be generated to assess the impact of anti-modakafusp alfa antibodies on the pharmacokinetic profile, drug efficacy, pharmacodynamic profile, and clinical safety will be evaluated, if possible. These analyses will be exploratory in nature and may be included in CSR if there is a trend.

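### SAP 7.10.3 reports pharmacodynamic results only if an undefined trend appears, which filters out null findings and departs from Protocol 13.6

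*SAP*

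**What the plan says.** SAP 7.10.3 plans that "several biomarkers will be assessed to test for their correlation with safety and efficacy, if possible", and adds exploratory analyses of dose and serum exposure against safety and efficacy. It closes with the rule that "A pharmacodynamic analysis will be included in CSR only if there is a trend". No statistic, threshold, direction or decision-maker is attached to the word trend.

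Protocol 13.6, on the same subject, says: "Markers of immune system activation will be summarized using descriptive statistics. Individual data will be listed". It adds that the summaries are to be given for each phase and by dose. It attaches no condition on the result.

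SAP 7.11.1 separates two things. ADA incidence and titer are unconditional: "All ADA data will be listed", and "Percent of patients with positive ADA at baseline and at any post-baseline time point during the study will be reported". The analyses of what ADA does to pharmacokinetics, efficacy, pharmacodynamics and safety are treated differently: "These analyses will be exploratory in nature and may be included in CSR if there is a trend".

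The by-subject listings in SAP Appendix A include drug concentrations, pharmacokinetic parameters, ADA, response data and adverse events. They include no pharmacodynamic or biomarker data.

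**The concern.** A reporting rule that depends on the result is decided after the data have been seen. If only apparent associations reach the report, a reader cannot tell how many relationships were examined and found flat, and so cannot judge how surprising the reported ones are.

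Null results would be informative here. Under SAP 4.1 the recommended phase 2 dose may be a pharmacologically active dose supported by pharmacokinetic/pharmacodynamic modelling, so a flat dose-marker relationship is something a reader of the report would want to see. Protocol 4.3.3 reports that six of eight patients with data were ADA positive after treatment, so the absence of a visible effect of ADA on exposure would also be worth stating. Protocol 9.3.15.2 requires fresh biopsies throughout phase 1b and in cohort III. Patients carry that burden whether or not a trend emerges.

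**Working it through.** The check is textual. Neither document gives a test, a significance level, a number of comparisons or a sample size for these analyses, so there is no figure to reproduce.

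1. **Does reporting depend on the result?** For pharmacodynamics, yes. The wording of SAP 7.10.3 is exclusive (only if), and the condition is a feature of the data, not of their availability.

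2. **Which results are removed?** The rule names no direction. An unfavourable association would qualify for inclusion just as a favourable one would. What it removes is the null result.

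3. **Is it consistent with the protocol?** Four sections bear on this.
   - Protocol 13.6: summaries and individual listings, unconditional. SAP 7.10.3 does not match this.
   - Protocol 13.7: presentation of pharmacokinetic/pharmacodynamic data in the report is optional, but is not tied to a trend.
   - Protocol 13.9: the effect of immunogenicity is to be examined where possible, with descriptive results. The condition is feasibility.
   - Protocol 9.3.15.4: biomarker samples are analysed if or when required. This governs whether an assay is run, not whether its result is shown.

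   The direct conflict is therefore with 13.6 alone.

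4. **Does another part of the SAP restore the null results?** None that is readable does. SAP 7.10.3 contains no unconditional marker summary. Appendix A lists no pharmacodynamic data. SAP 7.14 refers only to the version history in 1.2, which records no departure from Protocol 13.6.

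5. **How far does it reach?** By my count, six of the twelve exploratory endpoints in SAP 5.3 are pharmacodynamic: induced gene expression, cytokine fold-change, immune cell activation, CD38 occupancy, the type I interferon signature (which overlaps the first) and tumor immunophenotype.

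6. **Is the ADA wording the same?** No. SAP 7.11.1 says such analyses may be included, which does not bar reporting when no trend is seen, though it ties reporting to the result and leaves it optional even when a trend is present. There is also a genuine feasibility limit. With 6 of 8 positive, 8 − 6 = 2 patients are ADA negative. If that 75% rate held in a cohort of 25, the expected number of ADA-negative patients would be 25 × 0.25 = 6.25, or about 6. A comparison on that base could describe the data but could not establish the absence of an effect.

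**The case against.** The strongest defence is that the closing sentence of 7.10.3 follows text on correlation and exposure-response analyses, so it may be meant for those and not for the descriptive summaries of Protocol 13.6. Protocol 13.6 also does not name the study report as the place for its summaries. Both readings are possible. If the sentence is so limited, however, 7.10.3 contains no plan for the 13.6 summaries at all, Appendix A still omits the data, and the correlation analyses remain subject to a result-dependent rule.

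It is also fair that these are exploratory endpoints (Protocol 5.2.3, SAP 5.3) with descriptive or exploratory analyses. That limits the weight of the point but does not justify selecting on the result.

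Four stronger readings are tempting, and the documents do not support them.

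- *Only favourable results would be reported.* The rule has no direction; ADA lowering exposure, for example, would count as a trend.
- *ADA findings could be hidden.* ADA incidence and titer, the secondary endpoint, are summarised and listed regardless. Exposure, response and adverse events are listed by patient too. Only the summary of ADA impact is at risk.
- *The rule could distort the choice of pharmacologically active dose.* Protocol 13.7 has these data explored as they accrue, and Protocol 6.1.2 opens phase 2 only once the recommended dose is set. A rule on the content of the final report cannot change the data used earlier. It affects only whether readers can check the support for that choice.
- *A rate of false trends can be calculated.* That needs a threshold, a number of marker-outcome pairs and an assumption about their correlation. The documents give none of these.

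**Conclusion.** The point holds for SAP 7.10.3. As written, the rule makes reporting depend on an undefined feature of the result, filters out null pharmacodynamic findings and departs from Protocol 13.6. For SAP 7.11.1 it holds in a weaker form, confined to the ADA-impact analyses.

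The size is a matter of completeness of reporting, not of a number. It concerns exploratory pharmacodynamic endpoints, and leaves ADA incidence and titer and the choice of dose untouched. The conclusion assumes that the closing sentence of 7.10.3 covers the whole section. If it covers only the correlation analyses, the gap against Protocol 13.6 becomes an omission rather than a contradiction, and the remedy is the same. It is worth correcting because the correction is cheap.

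**What to change.** In SAP 7.10.3, delete the trend condition. State that the Protocol 13.6 summaries of immune-activation markers, by phase and dose, will be reported whatever they show and labelled exploratory. Where relationships with safety, efficacy or exposure are examined, state how many marker-outcome relationships were looked at.

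In Appendix A, add individual pharmacodynamic data to the listings.

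In SAP 7.11.1, replace the trend condition with one based on data availability, such as a minimum number of evaluable ADA-positive and ADA-negative patients, fixed before the data are reviewed. State there too how many relationships were examined.

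The cost is a few sentences in the SAP and some additional exploratory tables and listings. No trial procedure, sample or visit changes.

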7.11 Other Outcomes

7.11.1 Immunogenicity Analysis

The immunogenicity of modakafusp alfa will be assessed by determining anti-modakafusp alfa antibody incidence and characteristics (e.g., titer and specificity). All ADA data will be listed. For patients in the immunogenicity evaluable analysis set, percent of patients with positive ADA at each timepoint, as well as percent of patients with positive ADA by domain specific assay and ADA titers, will be summarized by dose levels by study phases (escalation and expansion). Percent of patients with positive ADA at baseline and at any post-baseline time point during the study will be reported. Additional summary tables and figures may be generated to assess the impact of anti-modakafusp alfa antibodies on the pharmacokinetic profile, drug efficacy, pharmacodynamic profile, and clinical safety will be evaluated, if possible. These analyses will be exploratory in nature and may be included in CSR if there is a trend.

7.12 Safety Analysis

7.12.1 Adverse Events

Adverse events will be coded using the Medical Dictionary for Regulatory Activities (MedDRA) Version 23.0 or later (based on version at time of database lock). Treatment-emergent is defined as any AE that occurs on or after the date of the first dose of any study treatment through 30 days after the last dose of any study treatment.

Treatment-emergent AEs will be summarized by MedDRA system organ class (SOC), and preferred term. For summary tabulations the following hematologic abnormalities coded to MedDRA preferred terms in the Investigations SOC will be pooled with the appropriate clinical terms in the blood and lymphatic system disorders SOC:

MedDRA Preferred Term (Investigation SOC)	Mapped to (Blood and lymphatic system disorders SOC)
Neutrophil count decreased	Neutropenia
Platelet count decreased	Thrombocytopenia
Hemoglobin decreased	Anemia
White blood cell count decreased	Leukopenia

Treatment-emergent AEs will also be summarized by the National Cancer Institute Common Terminology Criteria for Adverse Events (NCI CTCAE) version 5.0.

Summary tabulations will include the following categories:

- Treatment-emergent AEs.
- Drug-related treatment-emergent AEs.
- Grade 3 or higher treatment-emergent AEs.
- Grade 3 or higher drug-related treatment-emergent AEs.
- Grade 3 and Grade 4 TEAEs (based on maximum severity).
- Grade 3 and Grade 4 drug-related TEAEs (based on maximum severity).
- The most commonly reported treatment-emergent AEs (i.e., those events reported by $\geq 10\%$ of all patients in each phase or overall population as appropriate).
- Serious treatment-emergent AEs.
- Drug-related serious treatment-emergent AEs.
- Treatment-emergent AEs resulting in discontinuation of study drug.
- Treatment-emergent AEs resulting in study drug modifications (including discontinuation, delay, reduction, and interruption).

- Treatment-emergent AEs resulting in dose delays.
- Treatment-emergent AEs resulting in dose reductions.
- Treatment-emergent AEs resulting in dose interruptions.
- TEAEs leading to death
- Treatment emergent AESI – all grades
- Treatment emergent AESI grade 3 and above
- Treatment emergent AESI grade 3 or 4
- Treatment-emergent AEs resulting in infusion rate reductions.
- Treatment-emergent AEs resulting in infusion interruptions.
- Serious treatment emergent AESI

All summaries will be by dose levels by phases (escalation, safety lead-in, and expansion) for patients in the safety analysis set.

Patients with the same AE more than once will have that event counted only once within each body system, and once within each preferred term. Patients with the same AE more than once will have the maximum intensity of that event counted once within each body system, and once within each preferred term.

Most commonly reported (at least 10% of all patients in each phase or overall population as appropriate) treatment-emergent AEs will be presented by preferred term only. Patients with the same AE more than once will have that event counted only once within each preferred term.

An overall summary TEAE table will include numbers and percentages of patients who had any TEAE, and qualified TEAEs: drug-related AE, not drug-related AE, grade 3 or higher TEAE, grade 3 or higher drug-related AE, serious AE (SAE), drug-related SAE, not drug-related SAE, SAEs leading to study drug discontinuation, AEs resulting in study drug discontinuation, and on-study deaths. On-study death is defined as deaths that occur between the first dose of study drug and up to 30 days after the last dose of study drug and deaths assessed related to study drug that occur 30 days after the last dose of study drug.

Most frequent, >5% of all patients in each phase or overall population as appropriate, non-serious TEAE will be presented by system organ class and preferred terms for clinical trial disclosure.

A by-patient listing of DLTs that occur during Cycle 1 of treatment will be presented by dose levels for all patients in the DLT evaluable set. Patients will be grouped by the dose level to which they were originally assigned, including those who receive subsequent treatment at a lower or higher dose level.

A by-patient listing of all deaths regardless of whether on study or not will also be presented. In this listing, on-study deaths will be flagged.

Adverse Events of Special Interest (AESI)

For modakafusp alfa, infusion-related reactions (IRRs) are designated as AESIs.

For pembrolizumab, the following AEs are considered AESIs:

- Pneumonitis.
- Hepatitis.
- Colitis.
- Nephritis.
- Dermatologic reactions.
- Myocarditis.
- IRR.
- Endocrinopathies, including thyroid disorders, adrenal insufficiency, type 1 diabetes mellitus, and hypophysitis.

